## **Assessments/Measurement Instruments**

### **a) Anamnesis:**

In the initial assessment, the volunteer's name, age, medical history, duration of sports practice, weight, height, and calculation of Body Mass Index (BMI) were collected. Additionally, the participants' skin phototype (Fitzpatrick scale) was determined.

### **b) Measurement of Blood Levels of Creatine Phosphokinase (CK):**

The analyses were carried out by a clinical analysis laboratory (LabCenter Diagnostics Integrates, Itu, SP, Brazil) in a blinded manner, meaning they were unaware of the therapies applied to each participant. Briefly, the athletes rested for about 10 minutes in a seated position before blood collection. The material was labeled, and the forearm was aseptically cleaned with 70% alcohol. Using a 25x8 multiple collection needle, a vein in the antecubital fossa was punctured, and a 5 ml vacuum collection gel tube was inserted for CK analysis. Subsequently, the measurement was performed on a Roche Hitachi 917 biochemical analyzer using enzymatic methodology. A biomedical professional from the laboratory, not involved in the study, assessed the results in U/L. This analysis was conducted at baseline (T1), i.e., before the muscle damage induction protocol, and at 24h, 48h, and 72h after (T3).

### **c) Delayed Onset Muscle Soreness (DOMS):**

The perception of Delayed Onset Muscle Soreness (DOMS) was assessed using the Numeric Rating Scale (NRS). The scale was numbered from 0 to 10, where 0 indicated the absence of muscle pain, and 10 indicated maximum muscle pain during a maximum voluntary contraction for knee extension in a seated position. The choice of NRS was based on its reliability and responsiveness, as reported by .

[figure not shown]
The location and extent (percentage area) of DOMS were assessed using a pain map (mapDOMS) using a body chart representing the human body from different views (frontal, lateral, and dorsal). Two variables, the extent and location of pain, were used following the approach proposed by . Briefly, the areas where athletes reported pain were marked and later measured in cm. The painted area was then calculated using ImageJ software, an open-source software created by Wayne Rasband at the National Institutes of Health (NIH) in 1987 . Finally, the painted area was calculated as a percentage (%) of the total area related to the lower limbs.

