### Muscle Damage Induction Protocol

The adopted muscle damage induction protocol followed the recommendations of ACSM  for trained individuals, which consists of 8-12 repetitions above 70% of the one-repetition maximum (1RM) with 1 minute of rest between sets and 2 minutes between exercises. The protocol consisted of 3 sets of 10 repetitions for each exercise, with emphasis on the eccentric phase of the exercise to induce microlesions in the muscle tissue, and it is described in Table 3.

**Table 3** – Muscle damage induction protocol

| Exercise              | Illustration                                                                 | Sets | Repetitions | Total Repetitions |
|------------------------------|-------------------------------------------------------------------------------------|-------------|--------------------|--------------------------|
| Squat                 |  | 3           | 10                 | 30                       |
| Leg Extension         |  | 3           | 10                 | 30                       |
| Stiff                 |  | 3           | 10                 | 30                       |
| Hip Extension (Cable) |  | 3           | 10                 | 30                       |

|                      |                                                                                    |   |    |    |
|----------------------|------------------------------------------------------------------------------------|---|----|----|
| Deadlift      |   | 3 | 10 | 30 |
| Copenhagen    |   | 3 | 10 | 30 |
| Nordic Curl   |   | 3 | 10 | 30 |
| Leg Press 45° |  | 3 | 10 | 30 |

---

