### STATISTICAL ANALYSIS PLAN (SUMMARY)

Primary endpoint: Serum CK levels (U/L) over time.

Secondary endpoints: DOMS (NRS and mapDOMS), SJ and CMJ jump heights (cm), and isometric knee extensor force (kgf).

Statistical tests:

- Normality (Shapiro–Wilk) and homogeneity (Levene).
- Two-way repeated measures ANOVA with Tukey post hoc (parametric).
- Friedman and Kruskal–Wallis (nonparametric when assumptions not met).
- Significance level:  $\alpha = 0.05$ .

Software: IBM SPSS Statistics v20.0.

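### The DOMS conclusion is stated for soreness in general, but its positive signal comes only from an NRS tied to seated knee extension; the whole-lower-limb pain map showed no significant effect, and pain location is announced but not analysed

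*Combined protocol and SAP*

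**What the plan says.** The section on DOMS assessment defines two instruments.

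- **NRS, 0 to 10.** Zero is absence of muscle pain; "10 indicated maximum muscle pain during a maximum voluntary contraction for knee extension in a seated position". No other provoking manoeuvre is described.
- **Pain map (mapDOMS).** Athletes mark frontal, lateral and dorsal body charts. The section states: "Two variables, the extent and location of pain, were used". The only quantity it then derives is a single one: "the painted area was calculated as a percentage (%) of the total area related to the lower limbs".

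The Statistical Analysis Plan (Summary) lists "Secondary endpoints: DOMS (NRS and mapDOMS), SJ and CMJ jump heights (cm), and isometric knee extensor force (kgf"). Neither it nor the Data Analysis section mentions location. The induction protocol (Table 3) has eight lower-limb exercises, performed "with emphasis on the eccentric phase of the exercise to induce microlesions in the muscle tissue".

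The abstract's Results name each scale and report the null pain-map finding. Its Conclusion does neither: it credits PBM-pre with less DOMS at 48–72 h and PBM-post with less DOMS at every time point from 24 to 72 h.

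**The concern.** A conclusion about DOMS without qualification tells the reader that soreness of the exercised limbs fell. The instrument with a positive signal was anchored to one manoeuvre that mainly loads the knee extensors. The instrument covering the whole lower limb detected nothing significant. A reader who takes only the conclusion would not know that there were two scales, that one was null, or that the other showed no significant between-group difference.

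The location statement adds a mismatch between methods and results. Location is the one recorded item that could show whether soreness lay in the region the NRS task provokes, and nothing in the analysis uses it.

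**Working it through.** No figure in the plan is disputed, so the check sets the sections side by side and then looks at the printed means.

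**1. What each scale showed.** The results print the ANOVA values in the form F(2,27) = 0.302. They are read here as p-values, because 0.044 and values below 0.001 are described as revealing an effect.

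| Scale | Coverage | Moment | Moment × treatment | Between groups at each time |
|---|---|---|---|---|
| NRS (Table 6) | pain in seated maximal knee extension | <0.001 | 0.044 | none significant |
| mapDOMS (Table 7) | % of lower-limb area | 0.302 | 0.423 | post hoc not run |

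**2. What the word reduced rests on.** Reported NRS comparisons with baseline at 24/48/72 h:

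- Sham: <0.001 / <0.001 / 0.027
- PBM-pre: 0.027 / 0.555 / 0.999
- PBM-post: 0.460 / 0.933 / 0.993

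The time points credited in the conclusion are those where an active arm's own rise was not significant. That is a within-arm result, not a comparison with Sham. The interaction of 0.044 says that the three time courses differ somewhere. It does not say which arm differs from Sham, or when.

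**3. Direction of the means.** Sham minus active, from Tables 6 and 7, with n = 10 per arm. Welch t = (m1 − m2)/√(s1²/10 + s2²/10), unadjusted and on the printed scale. Example, NRS for PBM-post at 24 h: (5.70 − 3.00)/√((2.05² + 2.00²)/10) = 2.70/0.906 = 2.98, p = 0.008.

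| Scale, arm | 24 h | 48 h | 72 h | Unadjusted p |
|---|---|---|---|---|
| NRS, PBM-pre | 1.90 | 1.40 | 1.50 | 0.098 / 0.140 / 0.173 |
| NRS, PBM-post | 2.70 | 1.80 | 1.10 | 0.008 / 0.076 / 0.304 |
| mapDOMS (points), PBM-pre | 4.13 | 4.78 | 2.12 | 0.247 / 0.061 / 0.420 |
| mapDOMS (points), PBM-post | 4.67 | 4.97 | 2.89 | 0.143 / 0.047 / 0.265 |

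All twelve differences favour the active arm. These tests only describe the printed means. They ignore multiplicity and the log10 transformation used for mapDOMS, and they do not replace the trial's own ANOVA and Tukey results.

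**4. Location.** The methods announce extent and location. The SAP summary and Data Analysis plan no location variable, and Table 7 gives one percentage per arm and time. Figure 6 is captioned as showing the groups over time, but the text calls it an example; the figure is not visible in the text reviewed. What can be said is that no location variable is planned, tabulated or tested.

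**The case against.** The strongest reply is that soreness was assessed beyond the quadriceps. mapDOMS is a listed secondary endpoint over the whole lower limb, it was analysed by arm and time, and its null result is in the abstract's Results. This stands. A reader might infer that the DOMS objective was answered for one muscle group only; the documents do not support that. What remains is that the Conclusion leaves out the wider measure.

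Three other strong readings also fail.

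- **That soreness elsewhere could not register on the NRS.** The knee-extension wording belongs to the anchor at 10. Nothing tells athletes to ignore pain felt in other muscles. The fair statement is that no manoeuvre specifically provoking the hamstrings, gluteals or adductors is described.
- **That the share of exercises sizes a bias.** Counting Stiff, Hip Extension (Cable), Deadlift, Copenhagen and Nordic Curl as aimed mainly at other muscles gives 5 × 30 = 150 of 8 × 30 = 240 repetitions (62.5%). The documents assign no target muscles, so this allocation is an assumption; it becomes seven of eight exercises if gluteal load in Squat and Leg Press counts. Share of repetitions is also not share of soreness.
- **That the scales contradict each other because they sample different muscles.** The means point the same way on both. The scales differ in the moment effect and the interaction, but one measures intensity and the other painted area on a log10 scale, which could explain this equally well.

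It is also fair to say that a regional breakdown would be unplanned and thin: ten athletes per arm, with standard deviations often near or above the mean in Table 7. It can only be exploratory.

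**Conclusion.** The point holds as one of reporting and scope, and it should be corrected. The DOMS conclusion goes beyond its evidence in three ways: it does not name the NRS or its manoeuvre, it omits the null whole-lower-limb result, and it claims a reduction although no between-group NRS difference was significant at any time. Narrowing the label alone would not be enough, because the third problem would remain.

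The opposite conclusion is not supported either. A non-significant mapDOMS result with ten athletes per arm does not show absence of effect, and at 24 h the means were 9.55% in Sham against 5.42% and 4.88%.

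The verdict assumes that the printed ANOVA values are p-values and that Figure 6 is an example, as the text says. It does not rest on any allocation of exercises to muscles. The endpoint is secondary.

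**What to change.** 1. Name the endpoint NRS soreness during maximal knee extension in the SAP, Table 6 and the abstract, and limit the DOMS conclusion to it.
2. State beside it that mapDOMS, over the whole lower limb, detected no significant time or time-by-treatment effect.
3. Replace the claim of reduction with what was found. For example: the NRS rise from baseline was significant in Sham at 24–72 h, in PBM-pre at 24 h only and in PBM-post at no time point; the moment-by-treatment interaction was p = 0.044; no between-group difference was significant at any time point.
4. Either report pain location by region, by arm and time, as a descriptive exploratory result, or delete the statement that location was used. The documents do not say whether the charts were kept, so the first option depends on that and needs rater time for blinded re-measurement.

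Items 1 to 3 are wording changes and need no new data. The price is a narrower DOMS claim.

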### **d) Muscle Performance Tests on Jump Platform:**

Vertical jumps were performed twice, and the mean value was used for the analyses. Initially, the athletes warmed up on a cycle ergometer for 5 minutes at over 90 rpm. To perform the vertical jumps on a jump platform (Cefise, SP, Brazil), participants kept their hands on their hips and received verbal commands to initiate the jumps. For the Squat Jump (SJ) test, the athlete started from a semi-squat position, maintaining this position for approximately 3 seconds before takeoff. For the Counter Movement Jump (CMJ) test, the athlete was instructed to initiate a downward movement (squatting) from a standing position, which was immediately followed by an upward movement leading to takeoff. The mean value of two jumps was used for subsequent analyses.

**e) Muscle Performance Test of Knee Extensors by Dynamometry:**

The manual dynamometry test was performed on the individual's dominant leg, as indicated by a previous study, using a portable dynamometer (Manual Muscle Test - Lafayette Instrument). The athlete was positioned in a seated position with legs hanging off the edge of a table, keeping the knee at approximately 90° of flexion, as illustrated in figure 2. All participants performed two maximum voluntary contractions, verbally encouraged during execution for five seconds, with a one-minute interval between contractions. The mean value, in kilogram-force (kgf), of the two contractions was used for analysis.

**Figure 2.** Positioning of the adapted test from^31. A) The test was conducted with the participant in a seated position, legs hanging off the edge of a table, maintaining the knee at approximately 90° of flexion. To minimize posterior thigh discomfort, a small wedge-shaped cushion was placed on the posterior aspect of the distal thigh, and a standard gait belt was used to stabilize the thighs on the table. During the test, participants kept their arms crossed to isolate the quadriceps muscle. A foam pad was positioned on the anterior aspect of the leg, where the dynamometer was placed, situated 5 cm proximal to the lateral malleolus, with the strap wrapped around a pad and the dynamometer secured against the leg of the table (B). Additionally, a small elastic wrap was placed between the leg of the table and the triceps surae muscle to minimize belt slack (A).

[figure not shown]
### f) 1RM Test

The 1RM (One Repetition Maximum) Test aimed to assess the maximum load an individual could use during the execution of a specific exercise. This test was conducted for the exercises included in the muscle damage induction protocol. Initially, a maximum load close to what was expected for the participant to endure was chosen. The test concluded when the individual completed only one full repetition of the movement with the determined load. Five attempts were made, with a 3-minute interval between each attempt.

### **Photobiomodulation (PBM) Protocol**

Photobiomodulation (PBM) was performed using a whole-body irradiation system (Joovv Elite System), consisting of 6 panels with 76 red LEDs ( $660\pm10\text{nm}$ ) and 74 infrared LEDs ( $850\pm10\text{nm}$ ), totaling 900 LEDs in an area of  $12,193\text{ cm}^2$  (Figure 3). Athletes were positioned in front of the device (20 cm away from the thigh region), wearing only swim shorts to expose the muscle area of the lower limbs, trunk, and arms, with a total irradiation time of 20 minutes (600 seconds for the anterior region, 600 seconds for the posterior region). The effective PBM dose applied to each region (anterior and posterior) was  $48.97\text{ J/cm}^2$ , with an irradiance of  $81.62\text{ mW/cm}^2$ . The Sham condition consisted of irradiation with the device without effective light emission. An investigator not involved in data collection and analysis performed all irradiations (Sham and effective). The order of treatments was determined through simple balanced randomization, as shown in Figure 1.

The application of PBM (effective and/or Sham) was performed after the muscle performance tests (protocol T1), in the pre and post-protocol of muscle damage induction, as illustrated in Figure 1. In all conditions, participants were blindfolded during treatments. All PBM parameters were measured beforehand using a power and energy meter (PM100D, Thorlabs Inc.) equipped with the S130C light sensor (area of  $0.70\text{ cm}^2$ ) and are described in Table 2.

**Figure 3.** Whole-Body Photobiomodulation using the Joovv Elite System, containing LEDs (light-emitting diodes) in the infrared range ( $850\pm10\text{nm}$ ) and red range ( $660\pm10\text{nm}$ ). A. Frontal irradiation; B. Dorsal irradiation.

**Table 2** – Irradiation Parameters

**Table 2. Irradiation Parameters**

[figure not shown]
| Manufacturer                                                            | Joovv                     |            |
|-------------------------------------------------------------------------|---------------------------|------------|
| Wavelength                                                       | Red                       | Infrared   |
| Central wavelength (nm)                                          | $660\pm10$                | $850\pm10$ |
| Number of LEDs (6 panels)                                        | 456                       | 444        |
| Beam area (<math>\text{cm}^2</math>) per LED                     | 2.54                      | 2.54       |
| Operational mode                                                 | Continuous                | Continuous |
| Body distance (cm)                                               | 20                        | 20         |
| Radiant power (mW):                                              | 31.85                     | 25.29      |
| Power density (<math>\text{mW}/\text{cm}^2</math>)               | 45.50                     | 36.13      |
| Irradiation time (front) (s)                                     | 600                       | 600        |
| Irradiation time (back) (s)                                      | 600                       | 600        |
| Energy density (front) (<math>\text{J}/\text{cm}^2</math>)       | 27.30                     | 21.67      |
| Energy density (back) (<math>\text{J}/\text{cm}^2</math>)        | 27.30                     | 21.67      |
| Total average radiant power (mW)                                 | $(31.85 + 25.29) = 57.14$ |            |
| Total average power density (<math>\text{mW}/\text{cm}^2</math>) | $(45.50 + 36.13) = 81.62$ |            |
| Total average energy density (<math>\text{J}/\text{cm}^2</math>) | $(27.30 + 21.67) = 48.97$ |            |
| Total area of six panels (<math>\text{cm}^2</math>)              | 12,193                    |            |

|                                                 |      |      |
|-------------------------------------------------|------|------|
| Distance from power meter (cm)           | 20   | 20   |
| Area sensor power meter (cm^2) | 0.70 | 0.70 |

### Muscle Damage Induction Protocol

The adopted muscle damage induction protocol followed the recommendations of ACSM  for trained individuals, which consists of 8-12 repetitions above 70% of the one-repetition maximum (1RM) with 1 minute of rest between sets and 2 minutes between exercises. The protocol consisted of 3 sets of 10 repetitions for each exercise, with emphasis on the eccentric phase of the exercise to induce microlesions in the muscle tissue, and it is described in Table 3.

**Table 3** – Muscle damage induction protocol

| Exercise              | Illustration                                                                 | Sets | Repetitions | Total Repetitions |
|------------------------------|-------------------------------------------------------------------------------------|-------------|--------------------|--------------------------|
| Squat                 |  | 3           | 10                 | 30                       |
| Leg Extension         |  | 3           | 10                 | 30                       |
| Stiff                 |  | 3           | 10                 | 30                       |
| Hip Extension (Cable) |  | 3           | 10                 | 30                       |

|                      |                                                                                    |   |    |    |
|----------------------|------------------------------------------------------------------------------------|---|----|----|
| Deadlift      |   | 3 | 10 | 30 |
| Copenhagen    |   | 3 | 10 | 30 |
| Nordic Curl   |   | 3 | 10 | 30 |
| Leg Press 45° |  | 3 | 10 | 30 |

---

### 3.7 Sample Size Calculation

The sample size ( $n=30$ ) was calculated a priori using GPower 3.1 software. It considered 3 groups, 4 assessment time points (immediately after the muscle damage induction protocol, and at 24h, 48h, and 72h after), a minimum effect size of 0.25, a test power of 80%, and a significance level of 5%, for comparisons through two-way repeated measures analysis of variance.

### STATISTICAL ANALYSIS PLAN (SUMMARY)

Primary endpoint: Serum CK levels (U/L) over time.

Secondary endpoints: DOMS (NRS and mapDOMS), SJ and CMJ jump heights (cm), and isometric knee extensor force (kgf).

Statistical tests:

- Normality (Shapiro–Wilk) and homogeneity (Levene).
- Two-way repeated measures ANOVA with Tukey post hoc (parametric).
- Friedman and Kruskal–Wallis (nonparametric when assumptions not met).
- Significance level:  $\alpha = 0.05$ .

Software: IBM SPSS Statistics v20.0.

